2.2. Rationale for the study design

Heterologous ChAdOx1-MVA prime boost regime

ADVANCE will investigate a vaccination regime comprising a simian adenovirus ChAdOx1 as a priming agent and an MVA vector as a boosting vaccine. Both viral vectors will encode the same antigen, the TAA 5T4. Previous studies have shown that heterologous prime-boost regimens (rather than homologous prime-boost regimes) employing different genetic vaccine vectors are better means to induce potent T cell responses in nonhuman primates and humans¹⁰⁻¹². Adenovirus vectors have attracted considerable attention as potential viral vectors for genetic vaccination given their favourable safety profile and potent transduction efficiency following intramuscular injection. However, the neutralising antibody response against adenoviral capsid proteins following adenovirus vectors injection limits the success of vaccination protocols based on multiple administrations of the same adenoviral serotype. This has led to the consideration of simian adenoviruses, which are not known to cause pathology or illness in humans and to which the prevalence of antibodies is low. There is already considerable clinical experience with this vector expressing influenza¹³ and tuberculosis antigens.

A therapeutic vaccine in the form of MVA.5T4 viral vector was originally developed by Oxford BioMedica Ltd under a trade name of TroVax® as a homologous prime boost vaccination regime and to date has been administered to over 600 cancer patients¹⁴⁻¹⁶ (details in section 2.4). More recently Oxford has developed a new MVA.5T4 vector with the same transgene insert, but expressed from a different likely more potent poxvirus promoter.

The ChAdOx1-MVA 5T4 vaccination regime has undergone the first clinical testing as a prostate cancer vaccine in the VANCE01 study, which was completed in May 2018 (NCT02390063). Preliminary data analysis from low- and intermediate-risk localised prostate cancer patients enrolled in this study to date have demonstrated that the vaccine has a good safety profile and elicits substantial T cell immunogenicity (section 2.5).

Selection of the 5T4 antigen as a prostate cancer vaccine transgene

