2.5. Previous clinical experience with ChAdOx1-MVA 5T4 vaccine

VANCE01 was the first phase I clinical trial to assess the safety and immunogenicity of ChAdOx1-MVA 5T4 vaccine. VANCE01 began in Oxford in June 2015 (NCT02390063) and completed in May 2018. It compares ChAd-MVA vaccination to MVA alone, with and without low dose cyclophosphamide in low- and intermediate-risk localised prostate cancer.

An initial clinical assessment of the vaccine has shown it to be both safe and immunogenic for cellular and antibody responses to the 5T4 protein. The study design and further details of this

trial are given below.

Randomised, open label trial

To date, 40 patients have been enrolled and 39 of these have completed the vaccination course comprising either a standard immunisation protocol of 3 immunisations given at 4 week intervals or an accelerated protocol of 2 immunisations given at a 1 week interval.

The majority of adverse events were mild in nature and the interim clinical safety review was satisfactory. Both ChAdOx1.5T4 and MVA.5T4 vaccines have been well tolerated in both the standard prime-boost and the accelerated prime-boost vaccination regimes. Systemic reactogenicity appears most pronounced following the accelerated vaccination regime after the MVA.5T4 boost, but all symptomatic manifestations have been self-limiting and quickly resolving. Derangements in clinical haematology and biochemistry have all been mild and transient in nature. No additional safety findings are apparent following vaccination in combination with low dose cyclophosphamide. There has been one serious adverse event (SAE) which was deemed unlikely to be related to the investigational medicinal products employed in this study.

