4.2.1 Vaccine formulation, storage and accountability

ChAdOx1.5T4

ChAdOx1.5T4 vaccine is an unlicensed medicinal product manufactured by the University of Oxford Clinical Biomanufacturing Facility (CBF), Churchill Hospital, Oxford. It is formulated in formulation buffer at a nominal concentration of 1.1×10^{11} vp/mL. The formulation buffer consists of 10mM Histidine, 7.5% sucrose, 35mM NaCl, 1mM MgCl₂, 0.1% PS80, 0.1mM EDTA, 0.5% EtOH, pH 6.6. The fill volume is 0.5-1.0 mL. The dose of ChAdOx1.5T4 to be used in this study is 2.5×10^{10} vp. It is manufactured, labelled and released under Good Manufacturing Practice conditions to the clinical sites by the CBF. All movements of the study vaccine between the CBF and the clinical sites will be documented. The vaccine is supplied as liquid in glass vials and is stored at -80C in a locked, alarmed, temperature monitored freezer prior to release to the clinical sites. Following shipment to sites, the vaccine is stored as above, however, short-term storage for up to 3 months at 2-8C is acceptable if required, based on the manufacturer's stability data to date.

MVA.5T4

MVA.5T4 vaccine is an unlicensed medicinal product that has not been administered to humans before. VANCE01 trial has made use of the biologically equivalent MVA.5T4 vaccine supplied by Oxford BioMedica (manufactured by Baxter), trade name TroVax®. The new batch of MVA.5T4

vaccine expresses the 5T4 antigen under control of the different poxvirus promoter. It has been manufactured under Good Manufacturing Practice conditions by IDT Biologika GmbH, Germany. MVA.5T4 is supplied as a frozen liquid formulation in 10mM Tris buffer 140 mM NaCl, pH 7.7 in 2.0 mL clear glass vials. The formulation titre is 2×10^9 pfu/ml, the final drug product titre is 1×10^9 pfu/ml. The fill volume is 0.55 mL. Further details relating to batch manufacture can be found in the MVA.5T4 IMPD.

To ensure consistency with the VANCE01 clinical trial and all previous University of Oxford trials using MVA vectored vaccines, the dose to be used in this study will be 2×10^8 pfu. The vaccine will be labelled and released under Good Manufacturing Practice conditions to the clinical sites by the CBF. All movements of the study vaccine between the CBF and the clinical sites will be documented. At CBF it is stored at -80C in a locked, alarmed, temperature monitored freezer prior to release to the clinical sites. Following shipment to sites, the vaccine is stored as above.

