9. STATISTICS

9.1. Sample size

This is a non-randomised multi-centre phase I/II study. The trial will be open label; given the objective nature of the measurements, this is unlikely to introduce significant bias in assessing key outcomes. Study ID will be assigned to participants in the order in which they are enrolled in the trial. The correspondence between the subject study ID and the treatment number/arm allocation will be noted down in the CRF and subsequently entered in the OpenClinica system.

The total number of subjects enrolled to the study will be 36: 12 subjects with low- or intermediate-risk localised or locally advanced prostate cancer and 24 subjects with metastatic disease.

In this adaptive design study, the sample size of each patient cohort is chosen to allow an initial descriptive report of the safety of the vaccine in combination with checkpoint blockade. In this study, we are targeting a 25% response rate to the vaccine in combination with PD-1 blockade in mCRPC patients. The sample size of 24 patients in Group 2 will require that 6 out of 24 treated patients will have a complete response, partial response or stable disease. The patient cohorts recruited to the KEYNOTE-199 study will serve as a control group for ADVANCE and 11% overall response rate to PD-1 blockade as a monotherapy will be compared with the response rate to the vaccine in combination with anti-PD-1 treatment in the ADVANCE patients.

The 12 patients in the surgical group will be compared for response rate to the 26 surgical subjects treated with the same vectored vaccines but no anti-PD1 in the VANCE trial. None of the 26 patients in VANCE showed a significant reduction in PSA levels during that trial. The

sample size of 12 is chosen to allow an initial descriptive comparison of response rates with and without anti-PD1 to help power any potential future trial.

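### Group 1's comparison with VANCE cannot isolate anti-PD-1, because the MVA product changed together with nivolumab although Section 9.1 calls the vaccines the same

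*Protocol*

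**What the plan says.** Section 9.1 sets the Group 1 comparator as "26 surgical subjects treated with the same vectored vaccines but no anti-PD1 in the VANCE trial". It reports that "None of the 26 patients in VANCE showed a significant reduction in PSA levels during that trial" and gives this purpose: "sample size of 12 is chosen to allow an initial descriptive comparison of response rates with and without anti-PD1". The result is meant to inform the power of a possible later trial. No test, alpha or decision rule is attached. The cohort rationale in Section 2.2 draws the same contrast, setting the combination against the vaccine given alone in VANCE01. Impact on PSA is a co-primary objective for Group 1 (Synopsis and Section 3).

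On the product, Section 4.2.1 says three things:

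- Of the product used in ADVANCE: "MVA.5T4 vaccine is an unlicensed medicinal product that has not been administered to humans before".
- Of the product used earlier: "VANCE01 trial has made use of the biologically equivalent MVA.5T4 vaccine supplied by Oxford BioMedica (manufactured by Baxter"). Its trade name is TroVax.
- Of how the newly made batch differs: this "vaccine expresses the 5T4 antigen under control of the different poxvirus promoter".

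The same section sets the MVA dose at 2×10^8 pfu for consistency with VANCE01. Section 2.2 describes a new vector whose transgene insert is unchanged; that insert is "expressed from a different likely more potent poxvirus promoter".

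On VANCE01 as a whole, Section 2.5 says: "It compares ChAd-MVA vaccination to MVA alone, with and without low dose cyclophosphamide". It reports 40 men enrolled, on either three immunisations at 4-week intervals or two immunisations one week apart.

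**The concern.** A historical contrast can be read as the effect of adding anti-PD-1 only if the background vaccine is the same on both sides. Section 9.1 asserts that it is. Sections 2.2 and 4.2.1 describe a new MVA construct on one side and the older product on the other. If the boost vaccine changes at the same moment as nivolumab is added, the contrast measures both changes together.

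At stake is the interpretation of the only external reference the protocol names for Group 1's co-primary PSA question, and the use made of it afterwards. A future trial of adding anti-PD-1 to this vaccine would be sized on the wrong quantity if the whole observed difference were taken as the anti-PD-1 effect.

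**Working it through.** **What each group received**

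| | Group 1, ADVANCE (n = 12) | VANCE comparator (n = 26) |
|---|---|---|
| MVA product | New vector, different promoter, first in humans (2.2, 4.2.1) | TroVax (4.2.1) |
| MVA dose | 2×10^8 pfu | Stated as consistent (4.2.1) |
| Nivolumab | 1 dose, all 12 men (4.3) | None (9.1) |
| PSA responders | To be observed | 0 (9.1) |

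The indicators for new MVA and nivolumab are 1 and 1 for every Group 1 man and 0 and 0 for every VANCE man. The two columns are identical, so no analysis of these 38 men can separate the two effects. Any other difference between the trials falls into the same contrast.

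**No plan figure to reproduce.** Section 9.1 gives no alpha, power or effect size for Group 1. The calculations below only illustrate the size of the problem. Response here means whatever Section 9.1 means by a significant PSA reduction.

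**What would look like a signal.** Fisher's exact test of x/12 against 0/26, two-sided. With zero control responders, the probability of the observed table is C(12,x)/C(38,x).

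- x = 2: 66/703 = 0.094.
- x = 3: 220/8436 = 0.026. The opposite extreme, 0/12 with 3/26, has probability 2600/8436 = 0.308, which is larger, so it adds nothing and p = 0.026.

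Three responders of 12 is therefore the smallest count that reaches a nominal p below 0.05.

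**How often the new MVA alone could produce that.** Let p be the response rate under the new MVA with no anti-PD-1 effect. The documents give no value, so 10% to 30% is assumed. P(X ≥ 3) = 1 − P(0) − P(1) − P(2), with X binomial (12, p).

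- p = 0.10: 1 − (0.282 + 0.377 + 0.230) = 0.111
- p = 0.20: 1 − (0.069 + 0.206 + 0.283) = 0.442
- p = 0.30: 1 − (0.014 + 0.071 + 0.168) = 0.747

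A nominally significant excess over VANCE would then appear 11% to 75% of the time with nivolumab contributing nothing.

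**Make-up of the 26.** With 0 of 26 responding, any subset of size m also has 0 of m, so selecting by regimen leaves the observed control rate at zero. Only its exact 95% upper limit, 1 − 0.025^(1/m), changes: 13% at m = 26, 25% at m = 13 and 46% at m = 6. The two smaller values of m are assumed, because the protocol gives no breakdown.

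**The case against.** The best defence is that the protocol does give grounds for treating the vaccines as the same: it calls the older MVA biologically equivalent, keeps the transgene insert and matches the dose. These grounds belong in any fair account. They do not settle the matter, because equivalence is hard to square with a promoter described as likely more potent, and the new product has no human data behind it.

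A second defence is that the comparison is explicitly descriptive, with no test or decision rule. That stands: no formal inference fails, and the protocol does not say in terms that the difference will be taken as a pure anti-PD-1 effect. But it does label the contrast as with and without anti-PD-1 and links it to powering, and that label is what the product change undermines.

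A reader might also infer that the VANCE comparator mixes regimens and that this mix biases the difference. The documents do not support that reading. Section 2.5 describes all 40 enrolled men, whereas Section 9.1 uses 26 without saying how they were chosen. They may already be ChAd-MVA recipients only. Section 2.5 also reports comparable immune responses for the two schedules and no gain from cyclophosphamide. Those are immune responses obtained with the older MVA, not PSA responses, but they are the protocol's stated basis for treating the schedules alike. As none of the 26 responded, no selection among them can move the observed difference.

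**Conclusion.** The point holds as a contradiction within the protocol about the MVA product, with a direct consequence for attribution. New MVA and anti-PD-1 are completely aliased in Group 1, and a difference from VANCE cannot be credited to anti-PD-1 alone. That conclusion needs no numerical assumption. The illustrative 11% to 75% rests on an assumed 10% to 30% response rate under the new MVA alone, which nothing in the documents confirms or excludes. It would be too strong to say that the new MVA is known to act on PSA.

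The upper limits of 13%, 25% and 46% should not be read as bias from the new MVA. They show the precision that a smaller comparator would lose. The unstated composition of the 26 is a secondary gap in reporting, not a demonstrated source of error.

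**What to change.** In Section 9.1, replace the claim that the vaccines are the same with a statement that the MVA product differs from the one used in VANCE01. Reconcile this with the equivalence statement in Section 4.2.1 and the promoter statement in Section 2.2. Describe any Group 1 difference from VANCE as the combined effect of anti-PD-1 and the new MVA, and state that it will not be used as an anti-PD-1-only effect when a later trial is powered. Bring the cohort rationale in Section 2.2 into line.

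Secondarily, say which VANCE01 arms and schedules supply the 26 men. Show those on a regimen matching Group 1 alongside the full 26, rather than restricting the comparison to them. Section 2.5 gives a two-week prime-boost interval for ADVANCE, while Sections 2.2 and 4.3 give one week for Group 1. These passages must be reconciled before a matching regimen can be defined.

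The cost is wording plus a tabulation of existing VANCE data. The downside is a weaker attribution claim.

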9.2. Analysis

A detailed statistical analysis plan (SAP) will be prepared and finalised with the study statistician before the first interim data analysis.

Data analysis of the following endpoints: safety, efficacy and immunogenicity will be assessed as detailed in Section 7. Safety data will be presented according to frequency, severity and duration of adverse events. Efficacy analysis will be primarily based on evaluation of ctDNA reduction, PSA response rate, radiographic progression-free and overall survival between metastatic PCa study arms. Immunogenicity will consist of descriptive analysis of cellular and humoral immune responses to the vaccine transgene in the circulation, focusing on the magnitude and qualities of T cell responses.

Exploratory analyses may also include, but are not limited to, the analyses described below:
Factors predictive of treatment benefit: baseline demographic, tumour status, haematological or immunological variables may be included as interactions with treatment in logistic, longitudinal or proportional hazards models of efficacy endpoints in order to assess their value as factors predictive of treatment benefit.

Factors predictive of immune response: baseline demographic, tumour status, haematological or immunological variables may be included as explanatory variables in models of qualitative and quantitative immunological endpoints in order to assess their value as factors predictive of immune response.

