1. SYNOPSIS

Trial Title	Phase I/II open label non-randomised safety and efficacy study of the viral vectored ChAd-MVA 5T4 vaccine in combination with PD-1 checkpoint blockade in low- or intermediate-risk localised or locally advanced prostate cancer and advanced metastatic prostate cancer
Trial identifier	ADVANCE
Trial Centres	
Centre for Clinical Vaccinology and Tropical Medicine Churchill Hospital, [name]
 
Urology Department Churchill Hospital Oxford University Hospitals NHS Foundation Trust [name]
 
Oncology Department Churchill Hospital Oxford University Hospitals NHS Foundation Trust [name]
 
Department of Oncology The Christie NHS Foundation Trust^[1] [name]^[2] [name]

Clinical Phase	Phase I/II
Trial Design	Open label, non-randomised
Trial Population	Men aged 18 years and over, diagnosed with low- or intermediate-risk localised or locally advanced prostate cancer scheduled for radical prostatectomy (RP), or diagnosed with metastatic prostate cancer
Planned Sample Size	
36 subjects Group 1: 12 subjects per group Group 2: 24 subjects per group
 
Group 1: Low- or Intermediate-risk localised or locally advanced prostate cancer patients scheduled for RP ChAd-MVA 5T4 vaccine (one cycle) plus 1 dose of anti-PD-1 mAb (nivolumab)

	Group 2: Metastatic prostate cancer patients progressing on the second generation anti-androgens (e.g. abiraterone or enzalutamide) ChAd-MVA 5T4 vaccine (two cycles) plus 3 doses of anti-PD-1 mAb (nivolumab)
Follow up Duration	6 months for surgery patients and 12 months for metastatic patients
Planned Study Period	Approximately 2 years

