4.3. Allocation to study groups and dosing regime

The 36 subjects will be recruited to the study: 12 patients with low- or intermediate-risk prostate cancer (Group 1) and 24 patients with metastatic prostate cancer (Group 2).

Group 1: Low- or intermediate-risk localised or locally advanced prostate cancer patients scheduled to undergo radical prostatectomy

12 subjects will be treated with ChAd-MVA.5T4 vaccination plus 1 dose of the anti-PD-1 monoclonal antibody Nivolumab

Week 0:	ChAdOx1.5T4	2.5×10^{10} vp	intramuscular injection
Week 1:	MVA.5T4	2×10^8 pfu	intramuscular injection
	Nivolumab	480mg	intravenous infusion

Group 2: Metastatic prostate cancer patients with disease progression on anti-androgen therapy with either enzalutamide or abiraterone

24 subjects will be treated with ChAd-MVA.5T4 vaccination plus 3 doses of the anti-PD-1 monoclonal antibody Nivolumab

Week 0:	ChAdOx1.5T4	2.5×10^{10} vp	intramuscular injection
Week 4:	MVA.5T4	2×10^8 pfu	intramuscular injection
	Nivolumab	480mg	intravenous infusion
Week 8:	Nivolumab	480mg	intravenous infusion
Week 12:	ChAdOx1.5T4	2.5×10^{10} vp	intramuscular injection
	Nivolumab	480mg	intravenous infusion
Week 16:	MVA.5T4	2×10^8 pfu	intramuscular injection

Compliance with Dosing Regimen

Administration of all vaccines and checkpoint inhibitor therapies will be undertaken by a delegated research nurse or investigator in the clinical research facility or oncology treatment suite of the respective study centres. All study treatments will be recorded in the CRF and the relevant accountability log by the research nurse or investigator. There are no self-administered investigational products involved in this study.

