7.2. Secondary endpoints and outcome measures

- Development or increase in anti-5T4 cellular responses following study treatment two weeks post last vaccination and at any time-point on the study. Measurement of T cell responses will be done by IFNy ELISPOT assay to measure T cell responses to tumour and control antigens. Descriptive statistical analysis will be conducted. Immune profile of the prostate (low- or intermediate-risk PCa patients only). Tumour-infiltrating immune cells in surgical specimens and pre-treatment archival diagnostic needle prostate biopsies will be compared. Immune cell density, phenotype and function and will be assessed by immunohistochemistry and digital image analysis of formalin fixed paraffin-embedded tumour tissue samples using a panel of cell surface and intracellular markers. Descriptive statistical analysis will be conducted.
- Radiographic progression-free survival rate as measured by MRI, CT scans or bone scintigraphy (metastatic PCa patients only). Fisher's exact test will be used to compare 6 and 12-month progression-free survival rates between study arms. In order to evaluate progression-free rate as a function of baseline time point, analysis will be conducted using

two different baseline values: date of randomization and one months post last study treatment.

- Overall survival will be assessed for each arm 6 and 12 months post enrolment using the Kaplan-Meier method and log-rank test for statistical significance (metastatic PCa patients only).

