7.3. Other endpoints and outcome measures

The following exploratory analyses will be performed based on initial immunogenicity assessment and sample availability:

- Detailed analysis of cognate CD4+/CD8+ T cell function and memory phenotype may also be performed by multi-colour flow cytometry to simultaneously analyse surface markers and intracellular production of other cytokines (e.g. IL-2, IFNy, TNF α). Frequencies of 5T4-specific immune responses will be summarised in tabular format for each study arm and for overall combined study. Descriptive statistical analysis will be conducted, and the continuous variables will be summarised using mean, standard deviation, median, minimum and maximum. Fisher's exact test will be used to compare the 5T4-specific T cell response rates between study arms.
- Up-regulation of PD-L1 expression in a primary tumour or metastatic lesion(s) following study treatment. Density of PD-L1 positive immune cells and epithelial cells will be assessed by immunohistochemistry and digital image analysis of matched tumour tissue specimens before and after study treatment. PD-L1 expression levels will be summarised in terms of means, standard deviations and ranges for each study arm.
- PSA related kallikreins level change secondary to study treatment. The level of kallikreins in the blood will be measured by a 4 kallikrein peptidases test⁴⁵. Descriptive statistical analysis will be conducted.
- Change in number of circulating tumour cells secondary to study treatment may be assessed by CellSearch or Adnatest⁴⁴.
- Immunologic antigen spreading to other prostate associated antigens following study treatment (metastatic PCa patients only). The detection of antigen spread to other prostate associated antigens and the identification of specific antigens recognized will be analyzed descriptively by IFNy ELISPOT assay or ELISA.

Additional assays may include but are not limited to:

- Treatment-induced cellular immune responses characterized by cultured ELISPOT assay
- Treatment-induced cellular immune responses characterized by T cell receptor sequencing
- Flow cytometry analysis of immune cells isolated from the blood and surgical specimens

- Measurement of anti-5T4 serum antibody levels by ELISA (using plasma from preparation of above PBMC sample)
- Profiles of gene expression in the blood and surgical specimens by RNA analysis
- DNA or RNA sequencing of blood and tumour specimens for identification of tumour-specific somatic mutations

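### Section 9.2 plans treatment-by-factor interactions that a design with one regimen per cohort cannot estimate, so a main effect could be mistaken for a predictive one

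*Protocol*

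**What the plan says.** The synopsis describes an "open label non-randomised" study. Section 4.3 gives one regimen to each cohort:

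- Group 1 (localised or locally advanced disease, before prostatectomy): "12 subjects will be treated with ChAd-MVA.5T4 vaccination plus 1 dose of the anti-PD-1 monoclonal antibody Nivolumab".
- Group 2 (metastatic disease): "24 subjects will be treated with ChAd-MVA.5T4 vaccination plus 3 doses of the anti-PD-1 monoclonal antibody Nivolumab".

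Among the exploratory analyses, section 9.2 says that baseline demographic, tumour, haematological or immunological variables "may be included as interactions with treatment in logistic, longitudinal or proportional hazards models of efficacy endpoints". The stated purpose is "in order to assess their value as factors predictive of treatment benefit". In section 7.3, "Fisher's exact test will be used to compare the 5T4-specific T cell response rates between study arms".

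Other current text also assumes arms to compare. The efficacy sentence of section 9.2 refers to "radiographic progression-free and overall survival between metastatic PCa study arms". For an endpoint limited to metastatic men, section 7.2 says that Fisher's "exact test will be used to compare 6 and 12-month progression-free survival rates between study arms". The same section plans a log-rank test for overall survival, again in metastatic men only, and uses the randomisation date as one progression-free-survival baseline. Section 7.1 plans a Fisher comparison of adverse event rates between arms.

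The only comparators named are external. Section 9.1 sets Group 2 against the 11% rate in KEYNOTE-199 and Group 1 against 26 VANCE subjects, in both cases for response rate.

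**The concern.** A factor is predictive when the effect of treatment differs across its levels. Estimating that needs at least two treatments in the same population. Each cohort here has one, so the planned model cannot answer the question that section 9.2 sets for it.

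What can be fitted is an association between the factor and outcome among treated men. If that appears under the section's heading, a marker that merely tracks outcome could be taken for one that identifies who gains from the vaccine and nivolumab. Section 2.2 presents this trial as support for a larger one, so such a marker could carry over into patient selection there. Reading a Group 1 versus Group 2 difference in T cell response as an effect of schedule or dose number could mislead in the same way.

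**Working it through.** Section 9.2 gives no sample size, power or error rate for these models, so there is no figure of the plan's own to reproduce.

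**1. Within a cohort.** Let T be treatment and X a baseline factor, with design matrix [1, T, X, T×X]. Every man in the cohort has T = 1, so the T column equals the column of ones and T×X equals X. Two distinct columns remain:

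- Group 1 (n = 12): 4 columns, rank 2.
- Group 2 (n = 24): 4 columns, rank 2.

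The interaction is not estimable in either cohort. This depends only on the columns of the linear predictor, so it holds equally for logistic, longitudinal and proportional hazards models (where the baseline hazard takes the place of the intercept).

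**2. Pooled.** With T set to group membership over 12 + 24 = 36 men, the matrix has rank 4 of 4 and the model can be fitted. By section 4.3, however, T then also stands for disease stage, prime-boost interval (1 versus 4 weeks), cycles (1 versus 2) and nivolumab infusions (1 versus 3). Entering both cohort and treatment, each with its product with X, gives 6 columns and rank 4. The pooled interaction is therefore one with disease stage and everything that travels with it. For progression-free and overall survival, pooling is not open at all, because section 7.2 limits both to metastatic men.

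**3. What a within-cohort main effect can show.** Suppose that in Group 2 the response rate is 38.8% with the factor and 11.2% without it.

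- If untreated men would have had the same two rates, the treatment effect is 0 at both levels of X, and X is purely prognostic.
- If untreated men would have had 11.2% at both levels, the treatment effect is 38.8 − 11.2 = 27.6 points with the factor and 0 without it, and X is predictive.

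Both give identical Group 2 data.

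**4. How often a purely prognostic factor would look positive.** Assumptions, not fixed by the protocol for these models: a binary factor split 12/12, and an overall response of 25% (the Group 2 target in section 9.1, borrowed for illustration). For odds ratio OR, p0 and p1 solve (p0 + p1)/2 = 0.25 and [p1/(1−p1)]/[p0/(1−p0)] = OR. The probability of two-sided p < 0.05 is the sum of Bin(i; 12, p0) × Bin(j; 12, p1) over all tables (i, j) that reach it.

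| OR | p0 | p1 | Fisher | Uncorrected chi-square |
|---|---|---|---|---|
| 1 | 0.250 | 0.250 | 1.5% | 4.4% |
| 3 | 0.151 | 0.349 | 9.1% | 18.3% |
| 5 | 0.112 | 0.388 | 18.9% | 32.9% |
| 10 | 0.070 | 0.430 | 36.6% | 54.3% |
| 20 | 0.041 | 0.459 | 53.3% | 71.0% |

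**5. The between-arm tests.** For 5T4 response and adverse events, the only available contrast is Group 1 versus Group 2: computable, but confounded as in step 2. For progression-free and overall survival there is one metastatic cohort and nothing to compare it with.

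**6. After correction.** With the treatment terms dropped, [1, X] has 2 columns and rank 2 in each cohort, so the association is estimable.

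**The case against.** The models are exploratory and optional, and a detailed SAP is to follow. No primary or secondary result, sample size or stopping rule rests on the sentence. All of that stands and keeps the point small. It does not remove it: the protocol itself names the analysis, and no SAP wording can supply the missing contrast.

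The external controls might seem to rescue the interaction. Pooling patient-level VANCE data with Group 1 would make one estimable, but the protocol plans no such pooling, and the comparison would be non-randomised.

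Four stronger readings are tempting and go too far:

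- A reader might infer that prognostic factors will be reported as predictive. Followed literally, the interaction simply drops out of a within-cohort model. Mislabelling needs the further step of presenting the main effect under that heading. It is possible, not stated.
- A reader might infer that the section 7.3 Fisher test fails in the same way. It does not. It validly tests whether two cohorts differ, and no text says that a difference will be read as a regimen effect.
- A reader might infer that the associations can be called prognostic. Step 3 of the working shows that one treated cohort cannot establish that label either.
- A reader might infer from the target of 6 responders that only about one covariate can be modelled. That is a rule of thumb that the protocol does not state. It does not carry over to longitudinal or proportional hazards models, and the target counts complete response, partial response or stable disease, not the PSA/ctDNA composite of section 7.1.

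**Conclusion.** The point holds as a minor one. Section 9.2 names an exploratory analysis that the design cannot deliver: none of the 12 or the 24 men contributes information on a treatment-by-factor interaction within his cohort, and a pooled version is an interaction with disease stage and all that differs alongside it. This follows from the allocation in section 4.3 and needs no assumption about the data. Only the table of probabilities rests on the assumed 12/12 split, 25% response and range of odds ratios.

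The consequence is a risk of misinterpretation in exploratory reporting. The same leftover comparative wording reaches more prominent places: the adverse event endpoint in section 7.1, the survival endpoints in section 7.2 and the efficacy sentence of section 9.2. These should be corrected together. The amendment log records that version 3.0 removed the control arm and randomisation, which probably explains the residue, but the conflict lies wholly within the current text.

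**What to change.** - **Section 9.2, exploratory models:** delete the reference to interactions with treatment. Retitle the analyses as baseline factors associated with outcome among treated men, fitted within each cohort for its own efficacy endpoints. State that predictive value cannot be assessed without a concurrent control.
- **Section 7.3:** report the 5T4 responder rate in each cohort with an exact 95% confidence interval, and call any Group 1 versus Group 2 difference descriptive only.
- **Section 9.2, efficacy sentence:** remove the comparison between metastatic arms and describe estimates in the single metastatic cohort.
- **Section 7.2:** replace the Fisher and log-rank comparisons with 6- and 12-month progression-free and overall survival estimates and confidence intervals for Group 2. Replace the randomisation-date baseline with enrolment, which section 6.1 already defines.
- **Section 7.1:** present adverse event rates by cohort, with any contrast descriptive, and remove the reference to randomisation in the definition of the pre-treatment ctDNA value.

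The cost is wording only, plus whatever approval step the amendment needs. No patients, visits or samples change, and every replacement analysis can be done with the data already planned.
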